## 2.6 Analysis of the key secondary objective

There are no key secondary objectives in this study.

## 2.7 Analysis of secondary efficacy objective(s)

No sufficient data were collected to assess the effect of ruxolitinib versus placebo on overall survival and time to progression, so that no secondary efficacy analysis will be performed in this study.

## 2.8 Safety analyses

For all safety analyses, the safety set will be used. All listings and tables will be presented by treatment group.

The overall observation period will be divided into four mutually exclusive segments:

**pre-treatment period:** from day of patient's informed consent (molecular pre-screen or main study informed consent) to the day before the first administration of study treatment

**on-treatment period 1:** from day of start of study treatment to minimum of (1) 30 days following the last date of study treatment in period 1 and (2) start of open label ruxolitinib in treatment period 2:

[Start date of study treatment; min(last date of study treatment in treatment period 1 + 30 days, start date of open label ruxolitinib in treatment period 2 – 1 day)].

**on-treatment period 2:** from start day of open label ruxolitinib to 30 days following the last date of study treatment in period 2:

[Start date of open label ruxolitinib in treatment period 2; last date of open label ruxolitinib in treatment period 2 + 30 days].

**post-treatment period:** starting at day 31 after last dose of study treatment.

On-treatment assessment is defined as any assessment reported in the on-treatment period 1 or 2.

Safety summaries (tables, figures) include data from the pre-treatment period (to display the baseline status) and the on-treatment period 1. Data from the on-treatment period 2 (if provided) and the post-treatment period (if provided) with the exception of deaths should not be included.

In particular, summary tables for adverse events (AEs) will summarize only on-treatment events, with a start date during the on-treatment period 1, the so-called *treatment-emergent* AEs for period 1.

However, all safety data (including those from the post-treatment period if provided) will be listed and those collected during the pre-treatment, treatment period 2 and post-treatment period will be flagged.

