7.1.2 Screening

[figure not shown]
Patients will be consented to the main study informed consent after obtaining a central confirmation of HMR positivity. There will be a 40 day screening period (Day -40 to -Day -1). Screening procedures are outlined in the visit evaluation schedule ([Table 7-1 \[A\]](#)).

Upon completion of all routine screening procedures and all other eligibility criteria including patient history, laboratory assessments, and symptom score assessments should be performed.

A bone marrow biopsy should be performed, unless adequate archival tissue is available for the patient from a procedure performed within the last 6 months prior to randomization. Biopsy specimen and marrow aspirate must be sent to a Novartis designated laboratory for central analysis. Upon receipt of the bone marrow biopsy grade confirming patient eligibility, the investigator must perform the MRI (or CT for applicable patients) scan and send to the central imaging laboratory for assessment the same day as the scan. MRI/CT should be performed within 7 days prior to randomization.

A patient who has a laboratory test result(s) that does not satisfy the entrance criteria may have the test(s) repeated. These tests may be repeated as soon as the investigator believes the retest result is likely to be within the acceptable range to satisfy the entrance criteria, but should be completed within 40 days of the original screening visit date. In this case, the subject will not be required to sign another ICF, and the original patient ID number assigned by the investigator will be used. In the event that the laboratory test(s) cannot be performed within 40 days of the original screening visit, or the retest(s) do not meet the entrance criteria or the patient's medical condition has change significantly during the screening phase so that the inclusion/exclusion criteria are no longer met, the patient is considered a screen failure.

A new ICF will need to be signed if the investigator chooses to re-screen the patient after a patient has screen failed. The subject number will remain unchanged and patient will be entered in the IRT as re-screen. All required screening activities must be performed when the patient is rescreened for participation in the study. An individual patient may only be rescreened once for the study.

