8.1 Adverse events

8.1.1 Definitions and reporting

An adverse event is defined as the appearance of (or worsening of any pre-existing) undesirable sign(s), symptom(s), or medical condition(s) that occur after patient's signed informed consent has been obtained.

For patients who sign the molecular pre-screening ICF, AEs which occur after signature of this consent will only be captured if they meet the definition of serious as outlined in [Section 8.2](#) and are reported to be causally related with study procedures (e.g. an invasive procedure such as biopsy). Once the main study ICF is signed, all AEs per the descriptions below will be captured in the Adverse Event CRF.

Abnormal laboratory values or test results occurring after informed consent constitute adverse events only if they induce clinical signs or symptoms, are considered clinically significant, require therapy (e.g., hematologic abnormality that requires transfusion or hematological stem cell support), or require changes in study medication(s).

Adverse events that begin or worsen after informed consent should be recorded in the Adverse Events CRF. Conditions that were already present at the time of informed consent should be recorded in the Medical History page of the patient's CRF. Adverse event monitoring should be continued for at least 30 days following the last dose of study treatment. Adverse events (including lab abnormalities that constitute AEs) should be described using a diagnosis whenever possible, rather than individual underlying signs and symptoms. When a clear diagnosis cannot be identified, each sign or symptom should be reported as a separate Adverse Event.

Adverse events will be assessed according to the Common Terminology Criteria for Adverse Events (CTCAE) version 4.03.

If CTCAE grading does not exist for an adverse event, the severity of mild, moderate, severe, and life-threatening, corresponding to Grades 1 - 4, will be used. CTCAE Grade 5 (death) will not be used in this study; rather, information about deaths will be collected through a Death form.

The occurrence of adverse events should be sought by non-directive questioning of the patient (subject) during the screening process after signing informed consent and at each visit during the study. Adverse events also may be detected when they are volunteered by the patient (subject) during the screening process or between visits, or through physical examination,

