laboratory test, or other assessments. As far as possible, each adverse event should be evaluated to determine:

1. The severity grade (CTCAE Grade 1-4)
2. Its duration (Start and end dates) (add or Ongoing at End of Study for NOVDD)
3. Its relationship to the study treatment (Reasonable possibility that AE is related: No, Yes)
4. Action taken with respect to study or investigational treatment (none, dose adjusted, temporarily interrupted, permanently discontinued, unknown, not applicable)
5. Whether medication or therapy was given (no concomitant medication/non-drug therapy, concomitant medication/non-drug therapy)
6. Outcome (not recovered/not resolved, recovered/resolved, recovering/resolving, recovered/resolved with sequelae, fatal, unknown) Delete for NOVDD Trials as outcome is not collected
7. Whether it is serious, where a serious adverse event (SAE) is defined as in Section 8.2.1.

All adverse events should be treated appropriately. If a concomitant medication or non-drug therapy is given, this action should be recorded on the Adverse Event CRF.

Once an adverse event is detected, it should be followed until its resolution or until it is judged to be permanent, and assessment should be made at each visit (or more frequently, if necessary) of any changes in severity, the suspected relationship to the study treatment, the interventions required to treat it, and the outcome.

[figure not shown]
Confirmation of progression of disease, based on criteria described in [Section 10.4.1](#) should not be reported as adverse event. However death should be reported as SAE ([Section 8.2](#)).

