10.5.2.2 Adverse events (AEs)

Summary tables for adverse events (AEs) have to include only AEs that started or worsened during the on-treatment period, the **treatment-emergent** AEs. However, all safety data (including those from the pre and post-treatment periods) will be listed and those collected during the pre-treatment and post-treatment period are to be flagged.

[figure not shown]
The incidence of treatment-emergent adverse events (new or worsening from baseline) will be summarized by system organ class and or preferred term, severity (based on Common Terminology Criteria for Adverse Events [CTCAE] grades), type of adverse event, relation to study treatment by treatment group.

Serious adverse events, non-serious adverse events and adverse events of special interest (AESI) during the on-treatment period will be tabulated.

All deaths (on-treatment and post-treatment) will be tabulated.

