### **2.8.1 Adverse events (AEs)**

The incidence of treatment-emergent adverse events (new or worsening from baseline) will be summarized by system organ class and or preferred term, severity (based on Common Terminology Criteria for Adverse Events] grades, using CTCAE version 4.03), type of adverse event, relation to study treatment by treatment group.

Serious adverse events and non-serious adverse events during the on-treatment period will be tabulated.

All deaths (on-treatment and post-treatment) will be tabulated.

AEs will be summarized by number and percentage of subjects having at least one AE, having at least one AE in each primary system organ class (SOC) and for each preferred term (PT) using MedDRA coding. A subject with multiple occurrences of an AE will be counted only once in the respective AE category. A subject with multiple CTCAE grades for the same preferred term will be summarized under the maximum CTCAE grade recorded for the event.

In AE summaries the primary system organ class will be presented alphabetically and the preferred terms will be sorted within primary SOC in descending frequency. The sort order for the preferred term will be based on their frequency in the ruxolitinib arm.

The following adverse event summaries will be produced by treatment; overview of adverse events and deaths (number and % of subjects who died, with any AE, any SAE, any dose reductions/interruptions), AEs by SOC and PT, summarized by relationship (all AEs and AEs related to study treatment), seriousness (SAEs and non-SAEs), leading to treatment discontinuation, leading to dose interruption/adjustment, requiring additional therapy and leading to fatal outcome. In addition, for the summary of serious and non-serious adverse events the number of occurrences will be produced (an occurrence is defined as >1 day between start and prior end date of record of same preferred term

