#### 5.1.2 AE date imputation

Summary tables for adverse events (AEs) have to include only AEs that started or worsened during the on-treatment period, the *treatment-emergent* AEs. However, all safety data (including those from the post-treatment period) will be listed and those collected during the pre-treatment and after 30 days of post-treatment period are to be flagged.

Any missing onset date, causality, or severity must be queried for resolution. Unsolved missing values will be imputed according to the following:

- An unsolved missing causality will be left as missing.
- An unsolved missing severity will be left as missing in the AE tables. For AEs listed by highest severity, AE terms with missing severity will be excluded.
- An unsolved missing onset date will be imputed by the date of **Day 2**, which will force the AE to be treatment emergent, with the following exceptions:
  - If the stop/resolution date is prior to Study Day 1, the AE will then be considered as not being treatment-emergent.

- If both the month and day of the onset date are missing, and the last day of the year is prior to Study Day 1, the AE will then be considered as not being treatment-emergent.
- If only the day of the onset date is missing, and the last day of the month is prior to Study Day 1, then the AE will be considered as not being treatment-emergent.
- If only the day of the onset date is missing, and the 1st day of the month is after Study Day 1, the AE will then be considered as being treatment-emergent, and the incomplete date will be imputed as the 1st of the month.
- If the non-missing stop/resolution date is equal to Study Day 1, the AE will then be considered as not being treatment-emergent.

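### SAP 2.8 defines treatment-emergent AEs by start date alone, while SAP 2.8.1, SAP 5.1.2 and the protocol also count worsening; depending on how worsening is recorded, a screening-onset AE that worsens on treatment can be left out of the AE tables.

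*SAP*

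**What the plan says.** Four places define what enters the AE summary tables.

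- SAP 2.8 (Safety analyses): the tables "will summarize only on-treatment events, with a start date during the on-treatment period 1". The same sentence labels these the treatment-emergent AEs for period 1. Worsening is not mentioned.
- SAP 2.8.1 (Adverse events): "The incidence of treatment-emergent adverse events (new or worsening from baseline) will be summarized".
- SAP 5.1.2 (AE date imputation): the tables "have to include only AEs that started or worsened during the on-treatment period", with no restriction to period 1.
- Protocol 10.5.2.2: "Summary tables for adverse events (AEs) have to include only AEs that started or worsened during the on-treatment period".

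SAP section 4, on changes to protocol-specified analyses, is marked not applicable. The SAP's document history records that tables are confined to treatment period 1; it does not mention dropping worsening.

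Two protocol provisions determine whether an AE can start before dosing. Section 8.1.1: "Once the main study ICF is signed, all AEs per the descriptions below will be captured in the Adverse Event CRF". Section 7.1.2: "There will be a 40 day screening period". On follow-up of a detected AE, section 8.1.1 adds that "assessment should be made at each visit (or more frequently, if necessary) of any changes in severity".

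**The concern.** One set of tables has two definitions of treatment-emergent, in adjacent SAP sections. A programmer who follows SAP 2.8 literally filters on start date. One who follows SAP 2.8.1 also needs a rule for worsening, and the SAP supplies none: section 5.1.2 imputes onset dates and gives no worsening date or criterion.

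This matters because safety is a large part of what the terminated study still reports. PFS is not derived (SAP 2.5) and no secondary efficacy analysis is performed (SAP 2.7), while the frequency, duration and severity of AEs remain an endpoint of interest (SAP Table 1-1). If an AE that worsened on treatment fails the filter, it is missing from the tables by grade, relatedness, seriousness, discontinuation and dose change together.

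**Working it through.** No sample size, power or event figure is involved, so there is nothing to recompute. The check is to apply each definition to the possible AE histories.

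**Step 1. Can an AE start before the first dose?** Yes. AEs are captured once main consent is signed, and the screening period is up to 40 days. Conditions already present at consent go to Medical History instead (protocol 8.1.1).

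**Step 2. Apply the rules.**

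| AE history | SAP 2.8 | SAP 2.8.1, SAP 5.1.2, protocol 10.5.2.2 |
|---|---|---|
| Starts on treatment in period 1 | in | in |
| Starts in screening, never worsens | out | out |
| Starts in screening, worsens in period 1, one record with original start date | **out** | **in** |
| Starts in screening, worsens in period 1, worsening entered as a new record dated on treatment | in | in |
| Present at consent (Medical History), worsening recorded as an AE dated on treatment | in | in |

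Only the third row separates the rules. As an illustration, an AE noted at grade 1 in screening that reaches grade 3 on treatment, held as one record, is a grade 3 treatment-emergent AE under three texts and absent under SAP 2.8.

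**Step 3. Which recording convention applies?** The documents do not settle it.

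- Leaning towards one record: protocol 8.1.1 has severity changes assessed at each visit as part of following a detected event, and protocol 8.2.2 has progression of an SAE reported as follow-up to the original.
- Leaning towards several records: SAP 2.8.1 provides for a subject with more than one CTCAE grade under one preferred term, and SAP 2.8.1.2 has a rule for merging consecutive records of the same term whatever their severity. These are counting rules, not instructions for data entry.

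**Step 4. Is a date of grade increase available?** The AE attributes listed in protocol 8.1.1 are severity grade, start and end dates, relationship, action taken, therapy given, outcome and seriousness. A grade-change date is not among them. A worsening rule therefore has to work from what is recorded.

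**Step 5. Period restriction.** SAP 2.8 splits on-treatment time into periods 1 and 2 and tabulates period 1 only. SAP 5.1.2 refers to a single on-treatment period, as protocol 10.5.2.2 does. Read alone, it would admit period 2 events.

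**The case against.** The best reply is that this is loose wording with little effect. The SAP 2.8 sentence follows text that excludes period 2 and post-treatment data, so its main job may be to separate periods, and the AE-specific section that follows already includes worsening. If worsening is entered as a new record, nothing is lost.

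A reader might infer something stronger: that the start-date rule removes from the tables the cytopenias of most interest for this drug. The documents do not support that.

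- A cytopenia present at consent belongs in Medical History, and its later worsening is recorded as an AE, plausibly dated on treatment, although the start date to use is not stated.
- A laboratory abnormality counts as an AE only if it produces signs or symptoms, is clinically significant, or calls for therapy or a change in study medication (protocol 8.1.1). With hemoglobin above 10 g/dL required at entry, a mildly low screening value may not be an AE at all.
- SAP 2.8.3 tabulates CTCAE shifts from baseline to worst on-treatment value, lists newly occurring grade 3 or 4 values, and plots hemoglobin and platelets over time. All AEs are listed, with pre-treatment ones flagged (SAP 2.8).

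This limits the consequence but does not remove the conflict. The agreement of the four texts rests on an unstated data-entry convention. Laboratory shift tables carry no relatedness, seriousness or action taken, and do not cover non-laboratory AEs such as dizziness or headache. Listings keep the event visible but leave it out of the tabulated incidence.

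**Conclusion.** The inconsistency is real: SAP 2.8 conflicts with SAP 2.8.1, SAP 5.1.2 and protocol 10.5.2.2, and the departure from the protocol is not declared. Its consequence is conditional. An AE is lost from the tables only if it starts between main consent and first dose, increases in grade during on-treatment period 1, and keeps its original start date in a single record.

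The number of such AEs is unknown and cannot be estimated from the documents. The report is descriptive, so no test or formal conclusion is affected; what could change are AE counts and percentages. In a study stopped with few patients, one event can move a percentage visibly. The documents do not show that such events occurred, nor that worsening was dropped on purpose. The point should be settled before the AE tables are programmed, as a correction of definition.

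**What to change.** 1. In SAP 2.8, replace the start-date clause by: *events that started or worsened (CTCAE grade above the pre-treatment grade) during on-treatment period 1*.
2. Use the same words, limited to period 1, in SAP 5.1.2. SAP 2.8.1 then agrees as it stands.
3. State how worsening is identified from the recorded data. Where the worsening has its own record, use that record's start date. Otherwise, for an event continuing past first dose, use a maximum recorded grade above the pre-treatment grade.
4. If start date alone is intended, keep SAP 2.8, align SAP 2.8.1 and 5.1.2 to it, and declare the narrower rule in SAP section 4.

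The cost is wording in two SAP sections and a small change to the AE derivation. A single-record event may also need a site query, because its maximum grade does not by itself show that the increase came after first dose.

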### **2.8.1 Adverse events (AEs)**

The incidence of treatment-emergent adverse events (new or worsening from baseline) will be summarized by system organ class and or preferred term, severity (based on Common Terminology Criteria for Adverse Events] grades, using CTCAE version 4.03), type of adverse event, relation to study treatment by treatment group.

Serious adverse events and non-serious adverse events during the on-treatment period will be tabulated.

All deaths (on-treatment and post-treatment) will be tabulated.

AEs will be summarized by number and percentage of subjects having at least one AE, having at least one AE in each primary system organ class (SOC) and for each preferred term (PT) using MedDRA coding. A subject with multiple occurrences of an AE will be counted only once in the respective AE category. A subject with multiple CTCAE grades for the same preferred term will be summarized under the maximum CTCAE grade recorded for the event.

In AE summaries the primary system organ class will be presented alphabetically and the preferred terms will be sorted within primary SOC in descending frequency. The sort order for the preferred term will be based on their frequency in the ruxolitinib arm.

The following adverse event summaries will be produced by treatment; overview of adverse events and deaths (number and % of subjects who died, with any AE, any SAE, any dose reductions/interruptions), AEs by SOC and PT, summarized by relationship (all AEs and AEs related to study treatment), seriousness (SAEs and non-SAEs), leading to treatment discontinuation, leading to dose interruption/adjustment, requiring additional therapy and leading to fatal outcome. In addition, for the summary of serious and non-serious adverse events the number of occurrences will be produced (an occurrence is defined as >1 day between start and prior end date of record of same preferred term

#### **2.8.1.1 Adverse events of special interest / grouping of AEs**

Not planned for this premature termination study.

### **2.8.1.2 Adverse events of clinical trial safety disclosure**

For the legal requirements of ClinicalTrials.gov and EudraCT, two required tables on adverse events which are not serious adverse events with an incidence greater than 5% and on serious adverse events and SAE suspected to be related to study treatment will be provided by system organ class and preferred term on the safety set population.

If for a same patient, several consecutive AEs (irrespective of study treatment causality, seriousness and severity) occurred with the same SOC and PT:

- a single occurrence will be counted if there is  $\leq 1$  day gap between the end date of the preceding AE and the start date of the consecutive AE
- more than one occurrence will be counted if there is  $> 1$  day gap between the end date of the preceding AE and the start date of the consecutive AE

For occurrence, the presence of at least one SAE / SAE suspected to be related to study treatment / non SAE has to be checked in a block e.g., among AE's in a  $\leq 1$  day gap block, if at least one SAE is occurring, then one occurrence is calculated for that SAE.

The number of deaths resulting from SAEs suspected to be related to study treatment and SAEs irrespective of study treatment relationship will be provided by SOC and PT.

